*** Subject Population ***

Subject Population(s) Checklist

Select All That Apply :

- Adults
- Cognitively Impaired Subjects
- Employees (specifically targeted)
- Fetuses
- Minors (under 18)
- Neonates
- Non English Speaking Subjects
- Pregnant Women
- Prisoners
- Students (specifically targeted)
- Terminally Ill Subjects

Protocol Title: Conservative versus Suture Repair of Hand and Feet Lacerations in Children

Wards of the State

Other (any population that is not specified above)

*** Study Location ***

Study Location(s) Checklist

Indicate where the study will be conducted. Select all that apply:

Saint Louis University, Medical Center Campus

Saint Louis University, Frost Campus

Saint Louis University, Madrid Campus

Saint Louis University, SLUCare Practice Locations

SSM STL (DePaul Hospital, St. Mary's Health Center, St. Joseph (St. Charles, Wentzville, Lake Saint Louis), St. Clare)

 Cardinal Glennon Children's Medical Center

Saint Louis University Hospital (SSM Health- SLU Hospital)

SLU-SSM Cancer Center Research Alliance Sites

Other (In the box below, list any off-campus institutions or locations and describe the activities being conducted there. Please provide letters of cooperation and/or IRB approvals from each location to document support/approval of the study. You may provide such documentation as it becomes available, but you may not begin work at those sites until documentation of support is provided to the IRB.) Please refer to the Guidance for involving non-SLU institutions in human subject research.

*** General Checklist ***

General Checklist

Select All That Apply :

Collection of Specimens

Data collection via e-mail or the Internet

Deception/Incomplete Disclosure

Dietary Supplements, Vitamins, and Other Food Agents

FDA Approved Device

FDA approved drugs, reagents, other chemicals administered to subjects (even if they are not being studied), or biologic products

Genetic Testing

HIV Testing

Human blood, cells, tissues, or body fluids

International Research or Research on International Populations

Investigational drugs, reagents, chemicals, or biologic products

Investigational Device

 Investigator Initiated Study *?HELP?*

Protocol Title: Conservative versus Suture Repair of Hand and Feet Lacerations in Children

Medical Records

Photography, Video, or Voice-Recording Subjects

Questionnaires and/or tests

Radioisotopes/radiation-producing machines, even if standard of care

rDNA/Gene Transfer Therapy

Registry(ies)

Specimens to be stored for future research projects (must be in consent form)

Study of existing data or specimens

University Indemnified Study (SLU is responsible for liability coverage) *?HELP?*

Other (clarify in text box to the right)

Single Use. Provide a brief summary and justification for the Single Use Therapy. Note: This application will refer to research. For Single Use applications it is understood that 'research' will mean 'therapy'.

*** Funding ***

Funding Checklist

NONE

Funding - Saint Louis University

What type of Saint Louis University funding?	SLU eRS #
Departmental	61599

NOTE: Applicable grant application, contract or subcontract, investigator's brochure, and sponsor's protocol (for all industry sponsored clinical trials) must be attached. You will be prompted for these in section #16 (Attachments).

*** Expedited Paragraphs ***

To request an Expedited Review, check the appropriate category(ies) below. Provide justification for your request for Expedited Review.

Protocol Title: Conservative versus Suture Repair of Hand and Feet Lacerations in Children

To qualify for expedited review, research activities must (1) present no more than minimal risk to human subjects, and (2) involve only procedures listed in one or more of the categories below.

1. Clinical studies of drugs and medical devices only when condition (a) or (b) is met.
 - a) Research on drugs for which an investigational new drug application (21 CFR Part 31, 32) is not required. (Note: Research on marketed drugs that significantly increases the risks or decreases the acceptability of the risks associated with the use of the product is not eligible for expedited review.)
 - b) Research on medical devices for which
 - (i) An investigational device exemption application (21 CFR Part 812) is not required; or
 - (ii) The medical device is cleared/approved for marketing and the medical device is being used in accordance with its cleared/approved labeling.

2. Collection of blood samples by finger stick, heel stick, ear stick, or venipuncture as follows:
 - a) From healthy, nonpregnant adults who weigh at least 110 pounds. For these subjects, the amounts drawn may not exceed 550 ml in an 8-week period and collection may not occur more frequently than 2 times per week; or

From other adults and children, considering the age, weight, and health of the subjects, the collection procedure, the amount of blood to be collected, and the frequency with which it will be collected. For these subjects, the amount drawn may not exceed the lesser of 50 ml or 3 ml per kg in an 8-week period and collection may not occur more frequently than 2 times per week.

Children are "persons who have not attained the legal age for consent to treatments or procedures involved in the research, under the applicable law of the jurisdiction in which the research will be conducted."

3. Prospective collection of biological specimens for research purposes by non-invasive means.

EXAMPLES: (a) hair and nail clippings in a nondisfiguring manner; (b) deciduous teeth at time of exfoliation or if routine patient care indicates a need for extraction; (c) permanent teeth if routine patient care indicates a need for extraction; (d) excreta and external secretions (including sweat); (e) uncannulated saliva collected either in an unstimulated fashion or stimulated by chewing gumbase or wax or by applying a dilute citric solution to the tongue; (f) placenta removed at delivery; (g) amniotic fluid obtained at the time of rupture of the membrane prior to or during labor; (h) supra-and subgingival dental plaque and calculus, provided the collection procedure is not more invasive than routine prophylactic scaling of the teeth and the process is accomplished in accordance with accepted prophylactic techniques; (i) mucosal and skin cells collected by buccal scraping or swab, skin swab, or mouth washings; (j) sputum collected after saline mist nebulization.

Protocol Title: **Conservative versus Suture Repair of Hand and Feet Lacerations in Children**

4. Collection of data through non-invasive procedures (not involving general anesthesia or sedation) routinely employed in clinical practice, excluding procedures involving X-rays or microwaves. Where medical devices are employed, they must be cleared/approved for marketing. (Studies intended to evaluate the safety and effectiveness of the medical device are not generally eligible for expedited review, including studies of cleared medical devices for new indications.)

EXAMPLES: (a) physical sensors that are applied either to the surface of the body or at a distance and do not involve input of significant amounts of energy into the subject or an invasion of the subjects' privacy; (b) weighing or testing sensory acuity; (c) magnetic resonance imaging; (d) electrocardiography, electroencephalography, thermography, detection of naturally occurring radioactivity, electroretinography, ultrasound, diagnostic infrared imaging, doppler blood flow, and echocardiology; (e) moderate exercise, muscular strength testing, body composition assessment, and flexibility testing where appropriate given the age, weight and health of the individual.

5. Research involving materials (data, documents, records, or specimens) that have been collected, or will be collected solely for nonresearch purposes (such as medical treatment or diagnosis). (NOTE: Some research in this category may be exempt from the HHS regulations for the protection of human subjects. 45CFR 46.101(b)(4). This listing refers only to research that is not exempt.)

6. Collection of data from voice, video, digital, or image recordings made for research purposes.

7. Research on individual or group characteristics or behavior (including, but not limited to, research on perception, cognition, motivation, identity, language, communication, cultural beliefs or practices, and social behavior) or research employing survey, interview, oral history, focus group, program evaluation, human factors evaluation, or quality assurance methodologies. (NOTE: Some research in this category may be exempt from the HHS regulations for the protection of human subjects. 45 CFR 46.101(b)(2) and (b)(3). This listing refers only to research that is not exempt.)

8. [FOR IRB use only]. Continuing review of research previously approved by a convened IRB only when condition (a), (b), or (c) is met.

- a) Previously approved research where
 - (i) The research is permanently closed to the enrollment of new subjects;
 - (ii) All subjects have completed all research-related interventions; and
 - (iii) The research remains active only for the long term follow-up of subjects.
- b) Previously approved research where no subjects have been enrolled and no additional risks have been identified.
- c) Previously approved research where the remaining research activities are limited to data analysis.

9. [FOR IRB use only]. Continuing review or research not conducted under an investigational new drug application or investigational drug exemption where expedited categories two (2) through eight (8) do not apply but the IRB has determined and documented at a convened meeting that the research

Protocol Title: Conservative versus Suture Repair of Hand and Feet Lacerations in Children

involves no greater than minimal risk and no additional risks have been identified.

***** Background, Purpose, Study Procedures *******Title**

Conservative versus Suture Repair of Hand and Feet Lacerations in Children

Complete Sections 1 - 16. In sections that allow reference to sponsor protocol or grant, clearly state section and page numbers. Any information that is different or specific to the local site should be in the SLU application. Specify N/A as appropriate.

1. Background

Page numbers from a sponsor's protocol/grant may be referenced in 1a and 1b.

a) Provide an introduction and background information. Describe past experimental and/or clinical findings leading to the formulation of the study, if applicable. Investigator Initiated studies must cite references in the response provided or attach a bibliography. ***?HELP?***

Lacerations and accidental incisions are a common presenting complaint in Emergency Departments (EDs). According to the CDC, there were over 4 million ED visits in 2010 that involved suturing or stapling (1). A wound registry created by faculty at SUNY Stony Brook compiled a cohort of 1000 patients with wounds requiring sutures. Of their cohort, they found that 28% of these wounds were located on either the finger or hand (2). These numbers suggest that there are over 1 million hand and feet lacerations repaired at EDs in America every year. Traditional therapy for lacerations include suture repair with non-absorbable sutures and still remains the "gold standard" for repair and cosmetic outcome. In recent years, there have been numerous studies investigating alternative therapies to standard suture repair. Studies have shown non-inferiority of both absorbable sutures, topical adhesives, and adhesive strips in simple lacerations in both the adult and pediatric population (3,4,5,6). Studies in the biology of wound healing have shown that the three stages of healing, inflammation, epithelialization, and maturation, occur regardless of whether wounds were closed or left open (7,8). A recent study by Quinn, et al, in the general population showed no significant difference in cosmetic appearance and patient satisfaction of suture repair or conservative management (non-repair) in lacerations (9). There have also been investigations that challenge the past standards of care in pre-repair wound management. It has been observed that there was a decreased infection rate in suture-less laceration repairs, when compared to traditional suturing (10). The use of povidone-iodine as irrigation medium has been shown to delay wound healing and reduce wound strength (11). Running water has been shown to have equivalent infection rates as high-pressure irrigation with sterile saline (12). Another study found no increased infection rate when comparing sterile versus non-sterile technique in the repair procedure (13, 14). When you consider the time, cost, and pain involved in traditional suture repair procedures, a method decreasing all three of these factors without any increase in infection rates or decrease in patient satisfaction seems to be beneficial for both patients and the Emergency Departments that serve them. This earlier referred study by Quinn serves as the starting point for the current proposed investigation. This study found non-inferiority of suture versus conservative repair of simple hand lacerations, in both cosmetic outcomes and infection rates.

Please save frequently

b) Describe any animal experimentation and findings leading to the formulation of the study, if

Protocol Title: Conservative versus Suture Repair of Hand and Feet Lacerations in Children

there is no supporting human data.

n/a

2. Purpose of the study

a) Provide a brief lay summary of the project in <200 words. The lay summary should be readily understandable to the general public.

The purpose of this study is to compare outcomes of 2 repair methods in simple (<2cm) hand and feet lacerations in the pediatric population (2-17 yrs). Our hypothesis is that there is no statistical difference in cosmetic outcomes between suture repair and non-repair of these injuries. This study has been performed in the adult population, but has not yet been done in children. We would like to be the first to show that conservative repair can be done in our pediatric population. The suture group will have their injuries repaired with non-absorbable sutures (nylon) which remain the gold standard in cosmetic repair of hands and feet. The conservative group will have identical cleaning and preparation of the wound, but the laceration will be covered with antibiotic ointment and sterile gauze without repair. Secondary outcome measure include patient satisfaction, infection rates, pain during repair, time of initial ED visit stay, and cost of supplies used in repair. Our patients will return in 7-10 and 14 days and in 3 months for evaluation. Wounds and scars will be evaluated at both 7-10 and 14 days and 3-4 months by both the researchers and the parents or care givers. A satisfaction survey will be administered to the parent or guardian. At 3-4 months, digital photographs of the healing lacerations will be graded for appearance by clinicians blinded to the repair method. The initial visit will be billed to their insurance and the follow-up visits will be free (non-registered).

Page numbers from a sponsor's protocol/grant may be referenced in 2b and 2c.

b) List your research objectives (specific aims & hypotheses of the study).

Our primary hypothesis is that there is no difference in cosmetic outcomes between suture repair and conservative treatment of simple, superficial (<2cm) hand and feet lacerations in the pediatric population. Secondary measures will be infection rates, pain scores, time to return to normal activity, time of initial ED visit, and cost of supplies used in repair. Our aim is to show that conservative repair saves time, money and reduces patient pain compared to traditional suture repair, while having no decrease in cosmetic satisfaction or infection rates.

Please save frequently

c) Describe the study design (e.g., single/double blind, parallel, crossover, control, experimental, observational, etc.). If the study is investigator-initiated, a timeline for individual subject recruitment, follow-up, and analysis for the study is required. Also, indicate if the subjects will be randomized.

We will use a prospective clinical trial with computer generated randomization to test our hypothesis. Patients will be recruited by a qualified pediatric emergency physician. Once consent is obtained from the parent(s)/legal guardians, patient data will be collected. The patient will have their hand or foot laceration(s) treated in the emergency department at that time by an attending physician, PEM fellow, or senior resident. The patient will then follow-up in 10-14 days for a wound check and satisfaction survey, and then again at 3-4 months for repeat survey and photograph of the healed wound. Our timeline for recruitment is approximately 15-18 months, 12-15m for recruitment, plus 3 months for additional follow-up visits. Analysis of the data should take an additional month.

Protocol Title: Conservative versus Suture Repair of Hand and Feet Lacerations in Children

d) If subjects will be given placebo, please justify placebo use. *?HELP?*

There will be no placebos used in this study.

3. Study Procedures

a) N Is this project a multicenter study (i.e., same project is conducted elsewhere by a different investigator) OR does this study involve conduct of research at multiple sites? Is SLU acting as a coordinating center for other sites OR is the SLU PI a direct recipient of a federal grant for this research? If yes, complete and attach the Supplemental Application for Coordinating Center Activities.
Will the SLU site be participating in all parts/procedures/arms of the study?
If No, explain what SLU will NOT participate in:

Please save frequently

Page numbers from a sponsor's protocol/grant may be referenced in 3b, 3c, and 3d.

b) Describe all the procedures, from screening through end-of-study, that the human subject must undergo in the research project, including study visits, drug treatments, randomization and the procedures that are part of standard of care. Specify which procedures are for research and which are standard of care. Please note: The box below is for text only. If you would like to add tables, charts, etc., attach those files in the Attachment section (#16).

Once a patient is deemed eligible, based on a review of his or her medical record, he/she will be approached by one of the pediatric emergency physicians to participate in the study. English-speaking parents or legal guardians will be asked to sign the consent form on behalf of the minor. Emancipated patients will be asked to sign for their own consent. A computer generated randomized allocations schedule will be determined upon opening of the sealed enrollment packets containing the pre-assigned repair method. Once consent has been obtained, initial demographic and injury data will be collected (see Data Collection Sheet, Appendix A). Patients will be ineligible for study enrollment if the digits' ligaments, bone or vascular supply is compromised by the injury or if the attending physician determines the depth of the wound is too deep, often greater than 0.5cm for healing by secondary intention.

The wound will be prepared by the usual and standard ED protocol. Lidocaine-epinephrine-tetracaine (LET) gel will be applied to the wound on presentation. The wound will be irrigated under tap water for 1-2 minutes and direct pressure applied to dry the wound. For patients in the suture repair group, the wound will have local infiltration with 1% lidocaine with epinephrine. Sutures used will be 5-0 nylon. Bacitracin ointment and sterile gauze will then be used to cover and dress the wound. In the conservative group, no local anesthesia will be used after irrigation. Bacitracin ointment and sterile gauze will be used to cover and dress the wound. Standardized wound care instructions will be given to patients prior to discharge (see Wound Care Instructions, Appendix B).

Patients will be asked to follow-up in the Pediatric Emergency Department in 10-14 days. The patients will have a reminder phone call on day 6-8 for their follow-up visit and arrange for an appointment time. The wounds will be evaluated for complications that were defined a priori as follows: "wound infection" was one that required systemic antibiotics as determined by the treating attending physician; and "wound dehiscence" as a wound that required the placement

Protocol Title:

Conservative versus Suture Repair of Hand and Feet Lacerations in Children

of additional sutures or tissue adhesives. Children in the suture repair group will have their sutures removed. Parents will fill out a follow-up survey at this visit (see Initial Follow-up Survey).

Follow up data will be obtained from the parent or care giver for all subjects in the form of a questionnaire, patient with healing laceration will return with the parent or guardian for inspection of the wound with possible suture removal at 10-14 days then a re-evaluation of the healing wound with digital pictures taken at 3-4 months post ED enrollment for both treatment groups.

Patients will be asked to follow-up in the Pediatric Emergency Department in 12-16 weeks from the initial presentation. The patient will have a reminder phone call in week 11 for this visit and arrangement with time. The parent will fill out a second survey (see Final Follow-up Survey). Photographs of the wound will be taken, using a standardized protocol with a dedicated digital camera, and then printed by a pre-assigned printer. These photographs will be loaded to a computer to prevent alterations.

The photographs will be rated by 3 pediatric emergency physicians on the research team blinded to the treatment assignments. Independent evaluations will enable us to assess inter-observer reliability. The previously validated Visual Analogue Scale (VAS) will be used to assess the cosmetic outcome. The frequently used scale is a 100mm continuous line that is marked on the right end with "best scar" and on the left with "worst scar". The observer will be asked to mark on the line where they believe the scar "best fits". If the patient does not appear for their follow-up visit, a phone call will be made to the parent or guardian, who will be asked to report their satisfaction of the wound on a scale of 1 to 10, with 1 being "very unsatisfied" and 10 being "very satisfied".

c) If the proposed study is a clinical trial where a drug, vaccine, device or other treatment is compared to a placebo group or comparison treatment group, what are the guidelines or endpoints by which early decisions regarding efficacy or lack of efficacy can be made? For example, it may be reasonable to stop enrollment on a study when efficacy has already been clearly demonstrated, to avoid unnecessary enrollments of additional subjects. Alternatively, it may be reasonable to stop enrollment when it is clear that efficacy will never be demonstrated, given the statistical power of the study as designed. Describe the guidelines that are in place to assist in making these determinations, if relevant to the proposed study.

On an ongoing basis, we will evaluate potential complications and if we identify serious complications related to the study group, we will consider study termination.

d) Describe how data analysis will be performed (statistical tests, methods of evaluating data) and indicate the smallest group/unit for which separate reporting will occur. For studies involving a questionnaire, if data and reliability information are available, please describe or provide references. For full board, unfunded studies describe sample size determination and power analysis. If none, please justify.

Differences between groups will be analyzed using the Student's t-test for independent samples. Proportions will be compared using chi-square and the z-test for independent proportions. A significance level of 0.05 will be used in all analysis. Since this is an equivalence trial, a non-inferiority average difference of 15mm with the cosmesis VAS scale will be considered clinically equivalent. Previous studies have determined that the minimal clinically important differences between two groups ranged from 10 to 15mm (4,15,16).

A sample size of 18 patients per group will be needed to provide a power of 90% with 0.05 alpha error to detect a 15mm difference in the VAS. A patient attrition rate of 40% is expected and with this considered, a total of 50 patients will be enrolled in order to power the study this will include the 20 patients already enrolled in the previous study (#23300).

Protocol Title: Conservative versus Suture Repair of Hand and Feet Lacerations in Children

Please save frequently

e) State if deception (including incomplete disclosure of study purpose/procedures) will be used. If so, describe the nature of the deception and provide a rationale for its use. Also, describe debriefing procedures or justify a waiver of the requirement to debrief. NOTE: for studies using deception, an alteration of consent must be justified in the Informed Consent section of the protocol (#13) and the debriefing script/statement must be uploaded in the Attachments section (#16). See IRB Deception Guidelines.

f) Is there an accepted standard of care and/or standard practice at SLU for the condition/disease/situation being studied? This information will assist in comparing the risk/benefit ratio of study procedures relevant to usual care that would be received outside of the research context. *?HELP?* Y

If yes, please describe the standard of care and standard practice at SLU for the condition/disease/situation being studied.

The accepted standard of care for lacerations is suture repair. Recently, the type of sutures (absorbable versus non-absorbable) has been found to have equal efficacy. Studies have also shown comparable efficacy of topical adhesives and adhesive strips to close lacerations, but this is not yet accepted standard of care in most emergency departments. Although recent studies, including one at St. Louis University have shown non-inferiority of absorbable sutures when compared to non-absorbable, it has not yet become global standard of care.

g) Does this study involve any diagnostic imaging, labwork or genetic testing that could result in clinical discovery (diagnoses, genetic mutations, etc.)? Note that this could include discovery that is expected (related to the research) or incidental (not related to research aims, but possible, like a mass/shadow found in imaging despite not looking for it). N

If yes, please describe and include whether there are plans to share findings with study participants.

h) Is this study subject to the NIH Genomic Data Sharing Policy? N

The NIH GDS policy applies to all NIH-funded research that generates large-scale human genomic data as well as the use of these data for subsequent research and includes: genome-wide association studies (GWAS), single nucleotide polymorphisms (SNP) arrays, and genome sequence, transcriptomic, metagenomics, epigenomic and gene expression data, irrespective of NIH funding mechanism. Click here for more specific examples.

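### The aim of showing no loss of cosmetic satisfaction has no decision rule: the only margin is for the cosmesis VAS, and a non-significant difference test cannot support the claim

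*Combined protocol and SAP*

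**What the plan says.** Section 2(b) (research objectives) closes with an aim to show savings in time, money and pain "while having no decrease in cosmetic satisfaction or infection rates". The protocol does not define cosmetic satisfaction.

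Section 2(a) (lay summary) names satisfaction among the secondary outcomes: "Secondary outcome measure include patient satisfaction, infection rates, pain during repair". It lists this apart from the photographs graded by blinded clinicians. Sections 2(c) and 3(b) have the parent complete a survey at 10-14 days and again at 3-4 months. If a visit is missed, section 3(b) has the parent telephoned and asked to "report their satisfaction of the wound on a scale of 1 to 10".

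Section 3(d) (data analysis) gives these rules:

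- "Differences between groups will be analyzed using the Student's t-test for independent samples".
- Proportions are compared by chi-square and a z-test.
- "A significance level of 0.05 will be used in all analysis". Sidedness is not stated.
- The only margin: "a non-inferiority average difference of 15mm with the cosmesis VAS scale will be considered clinically equivalent".
- The only power statement, which is for a 15 mm VAS difference: "A sample size of 18 patients per group will be needed to provide a power of 90% with 0.05 alpha error". It is followed by 40% expected attrition and a total enrolment of 50.

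**The concern.** A claim that an outcome has not decreased is a no-worse claim. It needs a stated limit on the decrease that can be tolerated, and a confidence bound to set against that limit. For parent-reported satisfaction the plan supplies neither. It supplies only tests whose null hypothesis is no difference, and failing to reject that null is not evidence for it. Such a failure also becomes more likely as data are lost, so a smaller trial would find it easier to appear to meet the aim.

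Satisfaction is one of the two conditions that section 2(b) attaches to its message that conservative care saves time, money and pain. If a real loss of parent satisfaction went undetected and was summarised as no decrease, that message would be stronger than the data allow. This point concerns satisfaction only, not infection or the VAS comparison.

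**Working it through.** **1. The plan's own sample size.** Section 3(d) states 18 per group for 15 mm, 90% power and alpha 0.05, but no SD, so the figure can be neither reproduced nor refuted. Solving n = 2(z_alpha + z_power)² SD² / 15² for SD at n = 18 gives:

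- two-sided: 13.9 mm (13.5 mm with the exact t)
- one-sided: 15.4 mm (15.1 mm with the exact t)

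This calculation covers the VAS only. There is no counterpart for satisfaction.

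**2. Numbers per arm to examine.** Allocation is assumed 1:1.

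- All 50 respond: 50 / 2 = 25 per arm.
- The stated evaluable size: 18 per arm.
- 40% lost: 50 × 0.6 = 30, or 15 per arm.

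**3. Chance that a difference test misses a real drop.** Assumptions not in the documents: a true drop of 0.5 SD, and a score analysed by t-test. With df = 2n − 2 and noncentrality 0.5 × √(n/2), the miss rate is the probability that a noncentral t falls short of the critical value.

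| n per arm | noncentrality | missed, two-sided 0.05 | missed, one-sided 0.05 |
|---|---|---|---|
| 25 | 0.5 × √12.5 = 1.77 | 59% | 46% |
| 18 | 0.5 × √9 = 1.50 | 69% | 57% |
| 15 | 0.5 × √7.5 = 1.37 | 74% | 62% |

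**4. What a 95% CI would show.** Half-width in SD units = t(0.975, 2n − 2) × √(2/n):

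- 25 per arm: 0.57 SD
- 18 per arm: 0.68 SD
- 15 per arm: 0.75 SD

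All three exceed 0.5 SD, so even an observed difference of exactly zero would not exclude a drop of 0.5 SD.

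**5. Size needed for a formal no-worse conclusion.** With an illustrative margin of 0.5 SD, one-sided 0.025 and a true difference of zero, n = 2(z_0.975 + z_power)² / 0.5²:

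- 80% power: 63 per arm
- 90% power: 85 per arm

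At 25, 18 and 15 per arm the power is 41%, 31% and 26%.

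**The case against.** **Cosmetic satisfaction may mean the VAS.** Section 2(b) leaves satisfaction off its own list of secondary measures, and the only cosmetic endpoint in that paragraph is the primary one, which does have a 15 mm margin. If that is the meaning, the charge of a missing margin falls away and only a definition is needed. Against this, section 2(a) lists patient satisfaction separately, the background (section 1(a)) names cosmetic appearance and patient satisfaction as two things, and section 3(b) collects satisfaction from parents and the VAS from physicians. The parent-reported reading is the more natural one, but the ambiguity is real.

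**The instrument is not visible.** The follow-up surveys are listed among the attachments but not reproduced, and the 1-10 rating is only the fallback after a missed visit. If the survey item is categorical, the chi-square or z-test applies and the t-test figures do not. This objection stands against any result in points. It does not rescue the claim, because those too are difference tests.

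**The 15-per-arm figures may be too pessimistic.** The phone call exists to recover satisfaction when a visit is missed, so satisfaction data may stay nearer 25 per arm. The continuing review form ties its nine withdrawals to non-return for photographs and wound checks. This stands, and it favours the upper end of the sample sizes. Even there the miss rate is 46-59% under the stated assumptions.

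**No passage says that p > 0.05 will be read as no decrease.** That is correct. A reader might infer it from section 2(a), which frames the main hypothesis as an absence of statistical difference, but that sentence concerns cosmetic outcome. The defect is that the plan gives no rule that could support the satisfaction claim, not that it states a wrong one.

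**Conclusion.** The point holds in a limited form. On the parent-reported reading, section 2(b) makes a no-worse claim that nothing in section 3(d) can support. This follows from the text and depends on none of the assumed figures.

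The miss rates of 59-74% (two-sided) or 46-62% (one-sided) are illustrations. They rest on a 0.5-SD drop, a t-test and 1:1 allocation, and the range runs from no loss to the full 40% loss. A reader might take the two-sided range as an established property of this trial. The documents do not support that: they give no satisfaction SD, no important difference and no sidedness.

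A reader might also rescale the VAS margin to the 1-10 rating: 10 to 15 mm of 100 mm, applied to a 9-point range, gives 0.9 to 1.35 points. The documents do not support that either. Section 3(d) ties those values to the cosmesis VAS, and the 1-10 rating is only the phone fallback.

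Severity is minor. Satisfaction is a secondary outcome in a trial sized only for the VAS.

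**What to change.** - In section 2(b), say whether cosmetic satisfaction means the parent-reported outcome or the physician VAS. If it is the former, reword the aim as estimating the difference in parent-reported satisfaction between the arms.
- In section 3(d), add that this difference (conservative minus suture) will be reported with its 95% CI, as means or proportions according to the survey item, and that a non-significant difference will not be reported as no decrease.
- Keep a no-decrease claim only if the sponsor justifies a margin on the actual survey scale before the arms are compared. In that case make the claim only when the lower confidence limit lies above the limit set by that margin. Do not borrow a rescaled VAS margin.

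The cost is a few sentences, with no new patients or data. The downside is that the satisfaction result becomes descriptive and that a decrease will often not be excluded, given the interval widths in the working. Keeping the formal claim would be hard at this size.
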